#### **10.4.4 Safety Analyses**

NA

#### **10.4.5 Adherence and Retention Analyses**

We will calculate the Aim 1 co-design workshop attendance rate.

Adherence to the Aim 2 intervention will be assessed by the number of delirium assessments performed, the number of videos watched, and the daily DSD prevention management tasks logged. We will also calculate the retention rate (i.e., the number of participants who complete the study divided by the number of participants enrolled).

We will conduct an exploratory analysis to assess the dose effect, using a linear mixed model to examine caregiver knowledge gains, controlling for the degree of video completion. While not sufficiently powered, this analysis will provide preliminary estimates of the impact associated with degree of participation on caregiver knowledge, and will provide informative context for the results from the unadjusted analyses. Estimates will be reported with 95% confidence intervals to convey the precision of estimates.

#### **10.4.6 Baseline Descriptive Statistics**

Descriptive statistics will be calculated for all variables collected at the baseline/enrollment visit.

#### **10.4.7 Planned Interim Analysis**

Not applicable (NA).

CONFIDENTIAL

This material is the property of the NYU Langone Health. Do not disclose or use except as authorized in writing by the study sponsor

#### **10.4.7.1 Efficacy Review**

NA

#### **10.4.8 Additional Sub-Group Analyses**

NA

#### **10.4.9 Multiple Comparison/Multiplicity**

NA

#### **10.4.10 Tabulation of Individual Response Data**

NA

#### **10.4.11 Exploratory Analyses**

We will also track the usage of the intervention by secondary caregivers enrolled, if any. If enough secondary caregivers participate, we will also explore changes in their delirium knowledge and caregiving mastery outcomes.

### **10.5 Sample Size**

Aim 1 co-design workshop: We aim for 5-8 participants per session based on recommendations from Smaradottir et al. and our consultation with a Design Thinking expert from the Emory Roybal Center Design Studio. Accordingly, the target sample size is 8 caregivers (plus 8 on the waitlist).

Aim 2 feasibility trial: Because improvement in delirium knowledge should occur before improvement of caregiver mastery, our power calculation is based on delirium knowledge. Home health aides exposed to the current Aliviado videos demonstrated medium-to-large knowledge gains (Cohen's  $d = .64$ ). We will have 80% power to detect an effect of this magnitude in 26 caregivers, using a Bonferroni adjusted significance level of  $\alpha = .025$ . The expected gains will likely be larger, as previous research with a similar delirium intervention using telephone-based education modules found even greater improvement at 2 weeks (Cohen's  $d = .86$ ) and 2 months ( $d = .87$ ) post-intervention, and our projected sample of 26 will yield >99% power to detect similar effects. To allow for a 12% dropout rate and remain adequately powered, we aim to recruit 30 caregivers.

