## 10 Statistical Considerations

### 10.1 Statistical and Analytical Plans

Statistical considerations of this study are described in the following sections. However, given that this is a small feasibility trial, no additional formal Statistical Analytical Plan will be developed.

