### 10.2 Statistical Hypotheses

Primary hypothesis: The Aliviado DSD Caregiving Mastery Program will be feasible, acceptable and usable to family caregivers of persons living with dementia at risk for DSD.

CONFIDENTIAL

This material is the property of the NYU Langone Health. Do not disclose or use except as authorized in writing by the study sponsor

Secondary hypothesis: The Aliviado DSD Caregiving Mastery Program will improve caregivers' delirium knowledge and DSD caregiving mastery, as well as decrease caregiver strain, depression, and burden.

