#### **10.4.3 Analysis of the Secondary Endpoint(s)**

Paired t-tests will be performed to compare changes in delirium knowledge and caregiving mastery from baseline to 2 weeks (immediately post training), and changes in delirium knowledge, caregiving mastery, caregiver strain, depression, and burden from baseline to posttest (Week 6); effect sizes (Cohen's d) will be reported for all outcomes. To maintain the familywise error rate, we will use Bonferroni-adjusted alpha to determine significance.

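### Section 10.4.3 promises Bonferroni control over seven paired t-tests, but section 10.5 computes its 80% power at .025, a correction for only two

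*Combined protocol and SAP*

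**What the plan says.** Section 10.4.3 (combined protocol and SAP) sets out two groups of comparisons. For Week 2: "Paired t-tests will be performed to compare changes in delirium knowledge and caregiving mastery from baseline to 2 weeks". For Week 6: "changes in delirium knowledge, caregiving mastery, caregiver strain, depression, and burden from baseline to posttest (Week 6"). That is two tests plus five, seven in all, and the Protocol Summary lists the same seven. The section then adds: "To maintain the familywise error rate, we will use Bonferroni-adjusted alpha to determine significance". It does not say how many tests form the family or what the adjusted alpha is.

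Section 10.5 bases the sample size on delirium knowledge alone, with d = .64: "We will have 80% power to detect an effect of this magnitude in 26 caregivers, using a Bonferroni adjusted significance level of" .025. For the larger effects seen in a similar intervention (d = .86 at 2 weeks, .87 at 2 months) it says "our projected sample of 26 will yield >99% power to detect similar effects".

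Section 10.2 states directional hypotheses for all five secondary outcomes: improved "delirium knowledge and DSD caregiving mastery, as well as decrease caregiver strain, depression, and burden". Section 10.4.9, the multiplicity section, reads only NA. Section 10.1 says "no additional formal Statistical Analytical Plan will be developed".

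**The concern.** The correction promised in 10.4.3 follows directly on the list of seven tests, so a reader would take those seven as the family. The alpha in 10.5 is the one that results from dividing .05 by two. The protocol does not say which two tests are meant, and no later document is planned that could settle it.

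Two readings are open:

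1. The family is the seven listed tests. Each is then tested at .05/7, and the 80% in 10.5 is not the power of the planned test.
2. The family is two tests (for example knowledge at Week 2 and Week 6), or the correction is applied separately within each outcome. The 80% then stands, but error over the seven listed tests is not controlled.

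The choice decides results. A p-value of .015 would be significant under an alpha of .025 and not significant under .0071, and as written the choice could be made after the data are seen. The power figure also carries weight elsewhere: sections 5.6 and 10.5 justify the target of 26 completers by adequate power, and sections 5.6 and 5.7.2 commit to further recruitment until 26 have completed.

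**Working it through.** **Inputs**

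- Test: paired t-test on change scores (10.4.3)
- Evaluable n = 26; d = .64, with .86 and .87 as the larger effects; per-test alpha .025 (10.5)
- Tests listed: 2 at Week 2 + 5 at Week 6 = 7 (10.4.3)
- Overall alpha .05: not stated; inferred from .025 = .05/2
- Sidedness: not stated; two-sided inferred, as shown in step 1

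**Formula.** The test has df = n − 1 = 25 and noncentrality d√n. Power is the probability that a noncentral t variable with these parameters exceeds the two-sided critical value in absolute size.

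**Step 1: reproduce the plan's 80%.** Noncentrality is .64 × √26 = .64 × 5.099 = 3.263. At two-sided .025 the critical t is 2.385 and power is 80.4%. With n = 25 it is 78.5%, so 26 is the smallest n that reaches 80%. One-sided .025 would give 88.0%. The plan's figure is therefore the two-sided paired t-test at .025. The dropout step also agrees: 26/.88 = 29.5, rounded up to 30.

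**Step 2: correct for seven tests.** .05/7 = .00714, with critical t 2.930.

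| d | Noncentrality | Power at .025 | Power at .05/7 |
|---|---|---|---|
| .64 | 3.263 | 80.4% | 63.2% |
| .86 | 4.385 | 97.2% | 91.5% |
| .87 | 4.436 | 97.5% | 92.2% |

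The smallest d with 80% power at n = 26 rises from .637 to .747. At .05/7 and d = .64:

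- if all 30 enrolled caregivers complete, power is 72.4%;
- 80% needs 35 completers, or 35/.88 = 39.8, rounded up to 40 enrolled;
- one-sided testing gives 73.1%, so sidedness does not remove the gap.

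Taking only the five Week 6 tests as the family (alpha .01) gives 68.1% at n = 26.

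**Step 3: keep .025 and look at the error rate.**

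- All seven tests at .025: bound 7 × .025 = 17.5%. If the tests were independent, 1 − .975⁷ = 16.2%.
- Correction within each outcome (four knowledge and mastery tests at .025, three others at .05): bound 4 × .025 + 3 × .05 = 25%.
- Two tests only at .025: bound 5%, with five listed tests outside it.

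**Step 4: the claim of more than 99%.** At the stated two-sided .025, power is 97.2% (d = .86) and 97.5% (d = .87). Even at two-sided .05 it is 98.8% and 98.9%. Exceeding 99% at two-sided .025 with n = 26 needs d of about .945.

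**The case against.** The best defence is that section 10.5 restricts its calculation to delirium knowledge, that knowledge is tested at two time points, and that effects at two time points are cited in support. On that reading .025 is simply .05/2 for knowledge, and the 80% is right. This is plausible, but it is not written down. Knowledge and mastery at Week 2 would also give .025. Either way, five of the seven tests fall outside the control that 10.4.3 promises.

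A second point is sound: the conflict is specific to d = .64. Section 10.5 expects larger gains, and at d = .86 to .87 the sample of 26 has 91.5% to 92.2% power even at .05/7. The target of 26 is thus defensible for the effect the investigators hope for, but not as 80% power for the effect they used to set it.

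Third, 17.5% and 25% are worst-case bounds. With positively correlated outcomes (correlation .3 to .5 assumed) the rates would be nearer 13–15% and 18–20%. These are lower, but still well above 5%.

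Finally, this is a single-arm pilot with descriptive primary endpoints, and Cohen's d is reported for every secondary outcome whatever its p-value. That limits the consequence. It does not remove it, because the protocol states hypotheses for all five outcomes and section 4.2.2 intends them to support preliminary efficacy. The overstated 99% is a side issue of about two percentage points, with no effect on the design.

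**Conclusion.** The concern holds. The stated 80% is arithmetically correct at two-sided .025, but that alpha corrects for two tests while 10.4.3 lists seven and names no smaller family. At d = .64 and n = 26 the sponsor can have about 80% power with a two-test family, or 5% control over all seven tests with about 63% power, but not both. The claim of more than 99% power is wrong at the stated alpha and should read about 97%.

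This rests on an overall alpha of .05 and two-sided testing, both inferred. The gap persists under one-sided testing. The effect is confined to the secondary tests. It should be fixed before analysis.

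**What to change.** Name the family and the divisor in 10.4.3 and make 10.5 agree. Two coherent options:

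- **A. Seven-test family.** State alpha = .05/7 = .0071 for all seven tests. Restate power in 10.5 as about 63% at d = .64 and about 91–92% at d = .86 to .87. This keeps 10.4.3 and the hypotheses in 10.2 as written, at the price of a lower stated power. The claims of adequate power in 5.6 and 10.5 must then be reworded, for example by tying them to the larger effects.
- **B. Two-test family.** State that the controlled family is the two delirium-knowledge comparisons, each at .025, that the 80% applies to these, and that the other five tests are supportive only. Correct the 99% figure to about 97%. This keeps the 80%, but leaves mastery, strain, depression and burden, all with hypotheses in 10.2, without familywise-controlled significance. If the sponsor meant a different pair, name that pair instead.

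In either case replace NA in 10.4.9 with a reference to 10.4.3, and state the overall alpha and the sidedness.

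The cost is wording in 10.4.3, 10.4.9 and 10.5, plus 5.6 under A, with no added participants. Keeping both 80% power at d = .64 and seven-test control would take 35 completers (40 enrolled at 12% dropout), which is hard to justify when the primary endpoints are descriptive.

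### The power of more than 99% that section 10.5 claims for d = .86–.87 with 26 caregivers is about 97% on the basis that reproduces the section's own 80%

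*Combined protocol and SAP*

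**What the plan says.** Section 10.5 bases the Aim 2 power calculation on delirium knowledge. From home health aides who saw the existing videos it takes Cohen's d = .64 and states: "We will have 80% power to detect an effect of this magnitude in 26 caregivers, using a Bonferroni adjusted significance level of" .025. It then argues that gains will probably be larger, because a similar telephone-based delirium intervention "found even greater improvement at 2 weeks" (d = .86) and at 2 months (d = .87), and concludes that "our projected sample of 26 will yield >99% power to detect similar effects". That second statement gives no alpha, test, sidedness or standardizer of its own.

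The test is found in section 10.4.3, which plans paired t-tests on change from baseline and adds that "we will use Bonferroni-adjusted alpha to determine significance". Section 5.6 confirms 26 as the number of evaluable primary caregivers. Section 10.1 says that no separate statistical analysis plan will be written, so section 10.5 is the only account of the power calculation.

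**The concern.** The two power figures stand a sentence apart, share the same n and refer to the same outcome, and all three effect sizes are called Cohen's d and compared directly. A reader will take them as one calculation at two effect sizes. If so, the inputs that give 80% at d = .64 should give more than 99% at d = .86 and .87, and they do not.

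What is at stake is the reproducibility of a stated figure. The claim is a strict inequality and implies a type II error below 1%, whereas the calculation gives 2.5–2.8%. The discrepancy favours the design. It does not touch the primary endpoints (feasibility, acceptability and app usability), which are summarized descriptively with confidence intervals.

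**Working it through.** **Inputs**

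- n = 26 evaluable caregivers (sections 10.5 and 5.6).
- Alpha = .025, Bonferroni adjusted (section 10.5, attached to the 80% statement).
- Paired t-test on change (section 10.4.3).
- d = .64 for the 80% figure; d = .86 and .87 for the second figure (section 10.5).
- Two-sided testing: not stated, and inferred because it reproduces the 80%.
- Each d is the mean change divided by the standard deviation of change: not stated, and assumed.

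**Formula.** Power = P(T > c), where T is noncentral t with n − 1 = 25 degrees of freedom and noncentrality d√n, and c is the 1 − .025/2 quantile of central t on 25 df, c = 2.385. The opposite tail is negligible.

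**Step 1: the plan's 80%.** Noncentrality = .64 × √26 = 3.263; power = 80.4%. With 25 caregivers power is 78.5%, so 26 is the smallest n that reaches 80%. Allowing for dropout, 26 / (1 − .12) = 29.5, rounded up to 30. Both sample-size figures reproduce.

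**Step 2: the same calculation at the larger effects.**

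- d = .86: noncentrality .86 × √26 = 4.385; power = 97.2%.
- d = .87: noncentrality .87 × √26 = 4.436; power = 97.5%.

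A simulation with 400,000 runs per effect size gave 80.6%, 97.2% and 97.6% for the three values of d. The shortfall from the 99% bound is 99 − 97.2 = 1.8 and 99 − 97.5 = 1.5 percentage points.

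**Step 3: what 99% would need at two-sided .025.** It takes 31 evaluable caregivers (99.04% at d = .86, 99.17% at d = .87), or d of about .945 with 26.

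**Step 4: can another convention give both figures?**

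| Convention | d = .64 | d = .86 | d = .87 |
|---|---|---|---|
| Two-sided .025, t, n = 26 | 80.4% | 97.2% | 97.5% |
| Two-sided .025, normal approximation, n = 26 | 84.7% | 98.4% | 98.6% |
| Two-sided .05 (or one-sided .025), t, n = 26 | 88.0% | 98.8% | 98.9% |
| Two-sided .025, t, n = 30 | 86.7% | 98.8% | 98.96% |
| Two-sided .05, normal approximation, n = 26 | 90.4% | 99.2% | 99.3% |
| Two-sided .025, normal approximation, n = 30 | 89.7% | 99.3% | 99.4% |
| One-sided .05, t, n = 26 | 93.7% | 99.6% | 99.6% |

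None of these gives 80% in the first column and more than 99% in the other two. Sidedness does not rescue the claim. With the exact t-test and n = 26, the two-sided alpha needed for 99% is about .058 at d = .86 and .053 at d = .87, more than twice the stated .025. At those alphas d = .64 would have 89.4% and 88.5% power.

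**Step 5: a different standardizer.** If .86 and .87 are scaled by the raw-score standard deviation, with equal variances before and after and pre-post correlation r, the d on the change scale is d / √(2(1 − r)). Power at n = 26 and two-sided .025 is then:

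| r | d = .86 | d = .87 |
|---|---|---|
| .3 | 89.9% | 90.6% |
| .5 | 97.2% | 97.5% |
| .6 | 99.2% | 99.3% |
| .7 | 99.9% | 99.9% |

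Power reaches 99% at r = .586 for d = .86 and r = .576 for d = .87. If the same conversion were applied to .64, power there would be 87–88% instead of 80%.

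**The case against.** The strongest counter-argument concerns the standardizer. The effect sizes come from two sources, aides who watched the existing videos and caregivers in a telephone-based study, and published values of d need not share a scale. If .64 is on the standard deviation of change and .86/.87 are raw-score values, the 80% stands and the power for the larger effects exceeds 99% once the pre-post correlation is about .59 or higher. Nothing in section 10.5 requires all three values to be converted together, and the documents do not contain the data that would settle it. Sidedness is also unstated, and alpha is attached only to the first figure. So 97% is itself conditional.

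That condition stands, and it is why the correction must name its basis. It does not support the text as written. The plan gives no correlation and no conversion, and it ranks the three values against each other as one quantity. If a conversion was used, section 10.5 has to say so.

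The other objection is that the point hardly matters. The gap is under 2 percentage points in an optimistic scenario for a secondary endpoint, and no test, threshold or enrolment figure depends on it. That is fair, and it limits the point to a minor correction.

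**Conclusion.** The concern holds and is minor. On the only basis found that reproduces the plan's 80%, power with 26 caregivers is 97.2% at d = .86 and 97.5% at d = .87, which is 1.8 and 1.5 points short of the 99% that the text says is exceeded. This rests on two-sided testing, on the alpha of .025 carrying over to the second sentence, and on all three values of d being standardized by the standard deviation of change. Of these, the last is the one that could change the conclusion, and the documents neither state nor imply a different scale. The target of 26 evaluable and 30 recruited caregivers is unaffected.

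**What to change.** In section 10.5, replace the claim of more than 99% with about 97%, followed by a parenthesis: paired t-test, two-sided alpha .025, n = 26, d on the standard deviation of change. If the authors used another basis, they should instead state the test, sidedness, alpha, standardizer and any assumed pre-post correlation. They should then apply that basis to the 80% figure too, or explain why the cited effect sizes need different treatment. Before choosing, they should check which standard deviation each source used for its d.

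The cost is one figure and one short parenthesis. Sample size, enrolment and analysis stay as they are.

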### **10.6 Measures to Minimize Bias**

#### **10.6.1 Enrollment/Randomization/Masking Procedures**

NA

#### **10.6.2 Evaluation of Success of Blinding**

Not applicable.

#### **10.6.3 Breaking the Study Blind/Participant Code**

Not applicable.

## **11 Source Documents and Access to Source Data/Documents**

All data collected for this study will be maintained in an electronic format. All e-Consent and HIPAA documents will be collected and stored on the password-protected REDCap system with 2 factor-authentication. All surveys will be collected through online NYU REDCap survey questionnaires, cleaned, deidentified, and uploaded to a secure folder in PI [name]'s password-protected NYU Box research space with

CONFIDENTIAL

This material is the property of the NYU Langone Health. Do not disclose or use except as authorized in writing by the study sponsor

2 factor-authentication. Where there are unanticipated problems, adverse events or serious adverse events, the corresponding report forms will be filled out and maintained in REDCap. Protocol deviation forms will be filled out and maintained in a secure folder within PI [name]'s NYU Box research space for reporting purposes. PI [name] will be responsible for creating and maintaining an electronic study binder in REDCap. During weekly meetings, PI [name] and PI [name] will review all forms completed in the previous week to ensure accuracy, as well as edit/update the forms as needed. All corrections made will be recorded in a Data Management Log in a secure folder within PI [name]'s NYU Box research space and be updated and maintained by both PIs.

## **12 Quality Assurance and Quality Control**

Validation checks will be set up for all items in all electronic study forms and surveys. Survey data will be downloaded in csv or Excel format, deidentified, and cleaned in STATA and/or R on a weekly basis, uploaded to a secure folder within PI [name]'s NYU Box research space and then be reviewed during the weekly PI meeting to ensure accuracy. Descriptive statistics and graphs will be used to identify outliers and unusual values.

During the weekly PI meetings, the PIs will review the REDCap dashboard and verify that all forms are complete and on schedule; reasons for incomplete or delays in completion will be recorded in REDCap (and the Protocol Deviation Form if applicable). Any potential data entry errors will be discussed and corrected during the weekly PI meeting. All corrections made will be recorded in the Data Management Log. If needed, the PIs will reach out to participants to confirm their information accuracy.

Recordings from the co-design workshop (audio, video, live chat) will be encrypted and labeled only with a code number, which will be kept in a password-protected REDCap folder only accessible by the Principal Investigator and the co-Principal Investigator. Recordings will then be transcribed, deidentified and uploaded to a secure folder in PI [name]'s NYU Box research space with two factor authentication for later data analysis. PIs will verify accuracy of the transcripts and the original recordings may be consulted as needed.

## **13 Ethics/Protection of Human Subjects**

### ***13.1 Ethical Standard***

The investigator will ensure that this study is conducted in full conformity with Regulations for the Protection of Human Subjects of Research codified in 45 CFR Part 46.

### ***13.2 Institutional Review Board***

The protocol, informed consent form(s), recruitment materials, and all participant materials will be submitted to the IRB for review and approval. Approval of both the protocol and the consent form must be obtained before any participant is enrolled. Any amendment to the protocol will require review and approval by the IRB before the changes are implemented to the study. All changes to the consent form will be IRB approved; a determination will be made regarding whether previously consented participants need to be re-consented.

